2.4 Visit Structure

The visit structure and scheduled assessments are detailed in protocol section 6.7 (visit structure) and protocol section 17.2 (schedule of events and blood draws).

3 SAMPLE SIZE

Up to 19 patients, 3 active in Part 1 of the study and up to 16 randomised to active or placebo in Part 2, will be enrolled under this protocol. The sample size for this study was determined based on practical, and not statistical, considerations.

4 RANDOMISATION

Patients will only be randomised in Part 2 of the study. They will be randomised in a 1:1 fashion. There will be no stratification.

5 INTERIM ANALYSIS & REPORTING OF PART 1

No interim analysis is planned.

The decision to proceed to Part 2 will be determined through PI and an independent clinician review of the data for the first three patients up until the time that the third patient has completed the second week of the study. Medical History, Adverse Event, Concomitant Medication and Compliance data will be reviewed via the clinical database. A trend analysis will be carried out for the adverse events. No statistical outputs will be produced at this time, but the patients from Part 1 will be included in the same patient listings as for Part 2 as a separate group. Should the study be discontinued after Part 1, the listings described in the sections below will be produced for Part 1 only. The summary tables and figures described in the following sections relate to Part 2 only unless otherwise stated.

6 ANALYSIS PLAN

6.1 General

Summary statistics for continuous variables will consist of number of non-missing observations (n), mean, standard deviation (SD), minimum, 25th percentile, median, 75th percentile and maximum, unless specified otherwise. The precision of these variables is defined in the table, figure and listing shells document.

For categorical variables the number and percentage of patients in each category will be presented, based on the number of non-missing observations apart from disposition of patients, protocol deviations, background and demographic characteristics, prior and concomitant medications/procedures and adverse events where the percentage will be based on the number of patients in the analysis set.

Any statistical tests will be performed using a two-tailed 5% overall significance level, unless otherwise stated. The null hypothesis at all times will be that the treatments are equivalent. All comparisons between the treatments will be reported with 95% confidence intervals for the difference.

6.2 General Derivations

This section provides details of general derivations. Detailed descriptions of specific parameter derivations are provided later in the SAP.

• Definition of baseline

The Baseline value will be defined as the pre-dose value on Day 1, if that is missing or the first administration is not on Day 1, it will be defined from the most recent value available and recorded prior to the first administration of study treatment.

Incomplete dates

For calculation purposes, incomplete dates will be completed using worst case, the most conservative value possible. For example, if the start date has a missing day value, the first day of the month will be imputed for study day computations. If day is

missing for an end date, the last day of the month will be imputed. Similar logic will be assumed for missing month and year components.

• Methods for handling withdrawals and missing data

There will be no imputation of missing data. Screening data will be used if baseline is missing.

Statistical testing and graphical presentations will not be carried out for any given score or measurement if there are less than 5 results, for either the placebo or active group, for that score or measurement at any single time point.

6.3 Analysis Sets

The **Enrolled Set** includes all patients who passed screening irrespective of whether they received the study treatment.

The All Treated Set (ATS) includes all patients who have received study treatment.

The **Pharmacokinetic Analysis Set** (PK Analysis Set) includes all patients who take at least one dose of nomacopan and have at least one PK sample taken and analysed. This will be the primary population for assessing PK.

The **Safety Analysis Set** (SAF) includes all patients who received at least one dose of investigational product. This will be the primary population for assessing safety. Patients will be classified by the actual study medication they receive.

The following analysis sets apply to subjects in Part 2 of the study only:

- The **All Randomised Patients Set** (RAN) consists of all patients who were randomised, irrespective of the treatment they received, if any. If this analysis set coincides with the full analysis set, it will be omitted from the tables and listings.
- The **Full Analysis Set** (FAS) includes all patients randomised to treatment who received at least one dose of investigational product. This will be the primary population for assessing efficacy. Patients will be classified by the study medication they were randomised to.

The definitions for all analysis sets are sufficient to determine the patients included within these analysis sets and so do not require listing and agreeing prior to database lock. Actual study medication will be determined from the Study Drug Dispensing and Return Case Report Form (CRF) page.

6.4 Data presentations

The data will be summarised in tabular form by treatment group apart from disposition of patients, protocol deviations and background and demographic data which will be summarised by treatment group and overall patients.

The following treatment labels will be used "nomacopan 0.25% eye drops", "Placebo" and "Overall" (where applicable). For disposition of patients, "All patients" will be presented combining Part 1 and Part 2.

Only scheduled post-baseline visual acuity, clinical scoring, TBUT and categorical MMP-9 estimation will be tabulated, post-baseline repeat/unscheduled assessments will be disregarded, although they will be listed.

Analysis sets and study completion/withdrawal will be summarised using the enrolled set. Background and demographic characteristics will be summarised using the FAS. The efficacy endpoints will be summarised using the FAS. Prior/concomitant medications, administration of study treatment and exposure and safety will be summarised using the SAF. Pharmacokinetics will be based on the PK Analysis Set.

Eligibility listings will be based on the screened set and sorted by patient number.

Analysis set listings will be based on the enrolled set, PK will be based on the PK Analysis Set, safety listings and all other listings will be based on the ATS set.

Listings will be sorted by treatment group, patient number and date/time of assessment. Treatment groups will be presented in the following order: "Part 1, Treatment: nomacopan 0.25% eye drops", "Part 2, Treatment: nomacop

Graphical presentations of the data will also be provided where appropriate.

6.5 Disposition of patients

For Part 1 and Part 2, the number and percentage of all patients enrolled, included in the RAN, FAS, SAF, PK Analysis Set, who completed the study and prematurely discontinued the study, who completed study treatment and prematurely discontinued study treatment and study duration, will be summarised.

The number and percentage of patients will be summarised by their reasons for withdrawal from the study and study treatment.

Study duration will be derived as the number of days between date of starting drug administration and the date of study completion or the date of early study withdrawal. The date of starting drug administration will be determined from the Comfort Diary Card CRF page.

Eligibility for each of the analysis sets along with reasons for exclusion will be listed. Study completion/withdrawal data will be listed.

6.6 **Protocol Deviations**

Details of all protocol deviations (date, deviation category, specific details and classification of major or minor) and patient eligibility will be listed.

6.7 Background and Demographic Characteristics

6.7.1 Demography

Demographic characteristics (age, sex, ethnic origin and race) collected at Screening will be summarised along with indication (AKC, VKC, SAC, PAC), patient group (AKC/VKC and SAC/PAC) and country/site.

Age is calculated in years from the date of informed consent.

All patient demographic data including informed consent will be listed.

6.7.2 Medical History

Medical history events will be coded using the latest Medical Dictionary for Regulatory Activities (MedDRA) dictionary version. The version used will be indicated in the data summaries and listings. The number and percentage of patients will be presented for ongoing conditions and previous conditions separately by system organ class (SOC), and preferred term (PT), where SOC and PT will be presented in decreasing frequency of the total number of patients with medical history events. All events will be listed.

6.7.3 Ophthalmic History

The number and percentage of patients with any significant ophthalmic history will be presented for ongoing and previous conditions separately and also by condition, where conditions will be presented in the order: Cataract, Pseudophakia, Glaucoma, Glaucoma surgery, Eye lid surgery, Other surgery on the eyes, Other. All events will be listed.

6.8 Background Therapy and Concomitant Medications

Medications will be coded using the latest World Health Organization Drug dictionary (WHO Drug) version. The version used will be indicated in the data summaries and listings.

Prior medications are defined as those that started and ended prior to the first administration of study treatment. Medications that are ongoing at the first administration of study treatment or started after time of first administration will be deemed to be concomitant medications. If medication dates are incomplete and it is not clear whether the medication was concomitant, it will be assumed to be concomitant.

For Part 1 and Part 2, the number and percentage of patients taking concomitant medications will be summarised by medication class and standardised medication name, where medication class and standardised medication name will be presented in decreasing frequency of the total number of patients with medications. The number of patients receiving rescue therapy will be presented similarly (see section 6.10.3.3).

In summary tables, patients taking multiple medications in the same medication class or having the same standardised medication recorded multiple times in the study will be counted only once for that specific background therapy type, medication class and standardised medication name.

Background therapy and medication data will be listed together, where concomitant medications and background therapy as identified via the eCRF will be flagged. Background therapy diary card data will be listed.

6.9 Administration of Study treatment and Exposure

6.9.1 Compliance

For Part 1 and Part 2, the number of vials dispensed, the number of used vials returned, the number of vials expected to have been used and compliance for each patient will be summarised by treatment group.

 number of vials expected to have been used = 2 x (number of days that a subject administered eye drops dependent on date of first and last dose) where *number of days that a subject administered eye drops dependent on date of first and last dose* is derived from the Study Drug Dispensing and Return CRF page data as "date of final study drug return – date of first study drug dispensing". If a patient does not return their final dispensed study drug vials then the date of study competition/withdrawal will be used instead of date of return.

- compliance (vial return) = 100 x (total number of used vials returned / total number of vials expected to have been used)
- compliance (exposure) = 100 x (total number of doses administered / (total number of vials expected to have been used* 2)

The multiplication from 2 is required as each vial holds a dose per eye and the number of doses is counted per eye treated.

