6.3 Dosing Scheme

Part 1: The product will be supplied as a sterile 0.25% solution in 6 mL glass vials containing 1 mL of rVA576 solution. Single use eye dropper pipettes will also be supplied. The vials are for single use (one drop to each eye) and must be retained and returned to the site at each clinic visit.

Part 2: The product will be supplied as a sterile 0.25% solution in 6 mL glass vials containing 1 mL of solution of either rVA576 or placebo. Eye dropper pipettes will also be supplied. The vials are for single use (one drop to each eye) and must be retained and returned to the site at each clinical visit.

The patients will be randomised to receive either rVA576 active or placebo in double masked fashion. The product should be administered as one drop to each eye every 12 hours (i.e. twice daily) for a total of 56 days.

The product should be stored frozen in the site Pharmacy until the first 7 days' supply is to be given to the patient and then every 7 days thereafter. The product once unfrozen should be kept at 2 - 8 °C for a maximum of 7 days.

All patients entering the trial will have been on maximal topical therapy (meaning the maximal labelled dose or frequency of dosing) for at least three months before entry on the study and will continue on this therapy (background therapy) for the duration of the study.

Background therapy:

Patients should continue on whatever topical therapy they are on at the time of screening but this should remain stable during the trial. Lubricants and artificial tears may be used *ad libitum* but should not be administered for 15 minutes before or after the trial medication. In the event of worsening of signs or symptoms that, in the clinician's opinion is so severe as to necessitate a change of medication, ciclosporin and/or antihistamines may be introduced or increased in dose/frequency and this will be considered as a treatment failure for purposes of efficacy analysis. Topical corticosteroids may be added following introduction or increase in ciclosporin/antihistamine therapy if considered necessary.

See Concomitant Medications for further details of choice of eye lubricants.

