6.9.2 Exposure

For Part 1 and Part 2, the number of doses of study treatment administered (total number of occasions that a time of study drug was recorded) and the number of days of exposure to the study treatment ([last date of dosing - first day of dosing] + 1) will be summarised. These data will be obtained from the comfort diary card data.

All study drug dispensing and return data will be listed. The number of vials expected to have been used for each period will be presented. This will be calculated as 2 x (number of days that a subject administered eye drops dependent on date of first and last dose within each period)

where *number* of days that a subject administered eye drops dependent on date of first and last dose within each period is derived from the Study Drug Dispensing and Return CRF page data as "date of last study drug return for the period – date of first study drug dispensing for the period".

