6.10.3.3 Rescue therapy

The number and percentage of patients that received a rescue medication (as indicated on the Concomitant Medications CRF page) at any stage of the trial (during Day 1 to Day 56 (last dose) and during Day 56 to Day 84 (follow-up visit) to be presented separately) and the number and percentage of patients that were receiving a rescue medication at the end of the trial (indicated as ongoing on the CRF) will be presented in a summary table by treatment group.

The number and percentage of patients that received a rescue medication will be presented for each treatment group for Days 1 to 14, Days 15 to 28, Days 29 to 42 and Days 43 to 56 to compliment the intervals for the efficacy analysis. The percentage will be out of the number of patients at each timepoint who had data for comfort scores to be calculated.

A patient is considered to have taken rescue medication during an interval where the start date (Day 1 or later) occurs during that interval, or if they continue to receive rescue medication that started in a previous interval.

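### When the final vials are not returned, SAP 6.9.1 can count off-drug follow-up days as expected dosing, so a fully adherent patient may read about 67% on exposure compliance; the dose unit is also defined in two ways.

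*SAP*

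**What the plan says.** Protocol 6.3 sets the regimen: "The product should be administered as one drop to each eye every 12 hours (i.e. twice daily) for a total of 56 days". One vial serves both eyes at one session.

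SAP 6.9.1 sets expected vials at twice the number of days of administration and describes those days as depending on the first and last dose. It derives them, however, from dispensing and return dates: "date of final study drug return – date of first study drug dispensing". If the last vials are not returned, "then the date of study competition/withdrawal will be used instead of date of return" (the context shows that completion is meant).

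Two percentages follow. Vial-return compliance is used vials returned over expected vials. Exposure compliance is doses administered over twice the expected vials; the doubling is explained by doses being counted by eye.

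SAP 6.9.2 defines the number of doses administered, taken from the comfort diary, as the "total number of occasions that a time of study drug was recorded". Its days of exposure are "last date of dosing - first day of dosing] + 1", with dosing dates inside the bracket. For the listing of expected vials per supply period, 6.9.2 again uses return minus dispensing, without the extra day.

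**The concern.** The main problem is the fallback date. SAP 6.5 reports completing the study separately from completing study treatment. Protocol 17.3 places the end of dosing at Day 56 and a follow-up visit at Day 84, and SAP 6.10.3.3 presents rescue use "during Day 56 to Day 84 (follow-up visit") as its own interval. On that structure, study completion falls naturally about four weeks after the last dose. The fallback would then expect two vials a day over weeks in which no drug was due, against the section's own statement that the count depends on first and last dose.

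The second problem is the unit. The exposure numerator is described by eye in 6.9.1 and by recorded time in 6.9.2, while the denominator is always by eye.

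At stake is the SAP's compliance table in a trial whose primary objective is safety and tolerability. A reader who sees 67% or 51% for a patient who took every dose would misjudge how much drug was received.

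**Working it through.** The documents state no compliance percentage or expected vial count, so there is no plan figure to reproduce. The check applies the SAP formulas to a patient who takes every dose.

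**Inputs**
- 56 days, two sessions a day, one vial per session (Protocol 6.3): 2 × 56 = 112 vials, or 112 × 2 = 224 eye-doses.
- First dispensing on Day 1 and nominal return on Day 56 (Protocol 17.3).
- Follow-up on Day 84, ±7 days (Protocol 6.7 and 17.3): Day 77 to Day 91.
- Weekly supplies (Protocol 6.3) and two-weekly visits, so 7 or 14 days of vials could be outstanding at the end: 14 or 28 vials, leaving 98 or 84 returned.

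**Fallback date.** Expected vials = 2 × (completion day − 1). Exposure compliance = 224 / (2 × expected). Vial return = 98 or 84 over expected.

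| Completion day | Expected vials | Exposure, per eye | Vial return, 7 days out | Vial return, 14 days out |
|---|---|---|---|---|
| 77 | 152 | 224/304 = 73.7% | 98/152 = 64.5% | 84/152 = 55.3% |
| 84 | 166 | 224/332 = 67.5% | 98/166 = 59.0% | 84/166 = 50.6% |
| 91 | 180 | 224/360 = 62.2% | 98/180 = 54.4% | 84/180 = 46.7% |

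With 112 expected vials, exposure is 224/224 = 100%, and vial return is 98/112 = 87.5% or 84/112 = 75.0%. That remaining shortfall is true non-return and should show. If completion were taken as Day 56, exposure would read 224/220 = 101.8% and the problem would vanish.

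With 16 patients randomised 1:1, so 8 per arm, one patient reading 67.5% instead of 101.8% moves an arm mean by (101.8 − 67.5)/8 = 4.3 points.

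**Dose unit.** With the vials returned on Day 56, expected vials are 2 × 55 = 110 and the exposure denominator is 220. If the diary records one time per eye, the result is 224/220 = 101.8%. If it records one time per session, the result is 112/220 = 50.9%. Protocol 17.3 says only that the diary records when each administration took place. SAP 6.10.2.1 expects 140 comfort scores per 14 days, which is 14 × 2 × 5, or one set of five per session. That suggests session-level records but does not settle how dosing times are entered.

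**Missing extra day.** Against 110 expected, a patient with 110, 111 or 112 used vials in hand at the Day 56 visit reads 100.0%, 100.9% or 101.8%. Against 112 expected, the same patients read 98.2%, 99.1% or 100.0%. The choice is worth 0 to 2 points.

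**Agreement of total and periods.** If each return visit is also the next dispensing visit (Days 1, 14, 28, 42, 56), the 6.9.2 periods sum to 13 + 14 + 14 + 14 = 55 days, which matches the 6.9.1 total. Adding a day to the total alone breaks that match. Adding one to every period gives 59 days, because shared visit days are counted twice.

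**The case against.** The strongest reply is that the fallback is exceptional and its effect conditional. Protocol 6.3 and 6.7 require used vials to come back at every visit, so the substitute date should rarely be needed, and the SAP never says that completion is Day 84. Compliance is not an endpoint, defines no analysis set in SAP 6.3 and enters no model. Days of exposure come from diary dosing dates and are unaffected. With at most 19 patients and all dispensing and return data listed, an odd value would be noticed.

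Most of this stands, and it limits the size of the point. It does not remove it: a rule that may count off-drug days conflicts with the section's own description, and a listing that exposes a wrong percentage does not correct it.

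A reader might go further and infer that the formulas are wrong for every patient, with 102%, 67% and 51% all to be expected. The documents do not support that. The 102% needs all 112 vials in hand at the Day 56 visit, and the Day 56 evening vial may not have been used by then. The comparison with the inclusive exposure days in 6.9.2 is also incomplete, since the per-period vial formula in that section omits the extra day as well. The 51% depends on a diary layout that is not given, and 6.9.1 does state a per-eye count. The 67% needs per-eye counting and the 51% per-session counting, so the two cannot occur in one trial.

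**Conclusion.** The point holds in a limited form.

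- **Fallback date.** As written, it can add about 28 off-drug days and lower exposure compliance for a fully adherent patient to about 67% (62% to 74% over the follow-up window). Vial return falls to about 51% to 59% at Day 84, against a true 75% to 87.5%. This assumes that study completion means the follow-up visit, that doses are counted per eye, and that 7 to 14 days of vials are outstanding.
- **Dose count.** It is defined differently in SAP 6.9.1 and 6.9.2. The consequence, about 51% for every adherent patient whose vials are returned, follows only if one time is recorded per session.
- **Missing extra day.** This is minor, at 0 to 2 points.

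A reader might also infer that exposure, the primary safety analysis or the efficacy results are compromised. They are not: only the descriptive compliance summaries are affected.

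**What to change.** Three changes to SAP 6.9.1 and 6.9.2:

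1. When the final vials are not returned, end the expected-use interval at the last dosing date in the diary, and never let it run past the last dosing day. The study completion or withdrawal date should not be used.
2. Count administered and expected doses in one unit in both sections. Either use per eye throughout, stating how a recorded time maps to two eye-doses, or use per session throughout and drop the doubling.
3. If inclusive days are adopted, apply the convention to the 6.9.1 total and the 6.9.2 periods so that they agree. With shared visit days, this means adding the extra day once, for example in the last period, and not in each.

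With these changes, full dosing gives 100% exposure compliance. Vial return is 100% when all vials come back and otherwise falls only by the vials that are truly missing. The cost is SAP wording and programming; no data collection or trial conduct changes.
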